- ¹⁴ For patients not rolling over to the extension study: after the individual patient's end of the study, the investigator should report only any cancers of new histology and exacerbations of existing cancer, trial treatment related SAEs and trial treatment related AESIs of which the investigator may become aware of and only via the BI SAE form, please see section 5.2.6.2.1.
- ¹⁵ Duration of visits indicated in this Flow Chart are approximate estimates, actual time may vary as per site and patient requirements.
- ¹⁶ Visit 11 will be performed only by patients who prematurely discontinue trial drug but agree to continue trial participation. For patients who have permanently discontinued study medication the following procedures are no longer required: Dispense and administer IMP, IMP compliance check, AiCure review, PK Sampling, bio banking sampling.
- ¹⁷ If the patient permanently discontinues treatment early, the eEOT visit must be performed within 7 days of study drug discontinuation. The patient should be followed up according to guidance provided in section 6.2.3.4. For patients who permanently discontinue study medication the following procedures do not need to be performed: Dispense and administer IMP, IMP compliance check, AiCure review, PK Sampling, bio banking sampling and Physician Withdrawal Checklist at visit 10. For follow up of patients with Hb related issues, please refer to section 5.2.6.4
- 18 Safety follow-up visits must be completed after the EOT or early EOT visit. Each follow-up visit is to be scheduled from the EOT or early EOT visit (e.g. follow-up visit 1 should be conducted 7 days \pm 1 day from the EOT or early EOT visit).
- ¹⁹ Patients who finish the 26 weeks of treatment period in this study and the 4 weeks of safety follow-up, can rollover to the extension trial after completing follow-up visit 6.
- ²⁰ Study partner must complete the SCoRS and interviews at least at Visit 2 and EOT (please refer to inclusion criterion # 8)
- ²¹ Additional collection of the C-SSRS at an unscheduled visit may be done based on the investigator's discretion.
- X^H Haematology panel A and B only.

Page 8 of 112

Page 9 of 112

Proprietary confidential information © 2023 Boehringer Ingelheim International GmbH or one or more of its affiliated companies

TA	RI	\mathbf{F}	OF	CO	N	$\Gamma \Gamma N$	JTC
-1	DL	ינונ	v	,		יוניו	

TITLE I	PAGE	1
CLINIC	AL TRIAL PROTOCOL SYNOPSIS	2
FLOW (CHART	6
TABLE	OF CONTENTS	9
ABBRE	VIATIONS	13

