#### 6. GENERAL ANALYSIS DEFINITIONS

## 6.1 TREATMENT(S)

For basic study information on treatments to be administered, assignment of treatment groups, select of doses, see CTP Section 4.

Table 6.1: 1 lists the two treatment groups in this study. Table 6.1: 2 defines the analysing treatment period for safety analyses. For this study, the residual effect period (REP) is defined as 12 days after the last dose of trial medication.

Table 6.1: 1 Treatment descriptions

Long Name	Short Name	
Placebo	Placebo	
Iclepertin 10 mg QD	Iclepertin 10 mg	

Table 6.1: 2 Analysing treatment periods (same for all treatment groups)

Analysing Treatment Period	Start Date	End Date
Screening period	Date of informed consent	Date of the first treatment administration – 1 day
On-treatment period	Date of the first treatment administration	Date of the last treatment administration + REP
Post-treatment period	Date of the last treatment administration + REP + 1 day	Date of the last per protocol visit
Strictly on-treatment period	Date of the first treatment administration	Date of the last treatment administration
4-week withdrawal period	Date of last treatment administration + 1 day	Date of last treatment administration + 28 day

REP is the residual effect period which is defined as 12 days after the last dose of trial treatment.

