Visit 6	Week 12	85	78 – 119
Visit 8	Week 18	127	120 – 140
Visit 9	Week 21	148	141 – 161
Visit 10	Week 24	169	162 – 175
Visit 11	Week 26	183	≥176

All post-baseline actual day windows will be curtained at the end of residual period if earlier than the specified upper bound in the table.

Table 6.7: 8 Analysis visit windows for weight and vital signs (on-treatment period)

Analysis Visit	Nominal Week	Planned Day	Actual Day Window
Baseline		1	≤1
Visit 2	Week 0 (post-baseline)	1	2 – 56
Visit 5	Week 9	64	57 – 119
Visit 8	Week 18	127	120–175
Visit 11	Week 26	183	≥176

All post-baseline actual day windows will be curtained at the end of residual period if earlier than the specified upper bound in the table.

[figure not shown]
Table 6.7: 9 Analysis visit windows for clinical laboratory evaluations, weight, and vital signs (post-treatment period)

Analysis Visit	Nominal Week	Planned Day	Actual Day Window (days after last dose)
Follow-up 2	14 days post-treatment	EOT + 14 days	13 – 19
Follow-up 4	21 days post-treatment	EOT + 21 days	20 – 26
Follow-up 6	28 days post-treatment	EOT + 28 days	>27

This analysis visit windows only apply to the post-treatment period defined in Table 6.1: 2

Table 6.7: 10 Analysis visit windows for PWC-20

Analysis Visit	Nominal Week	Planned Day	Actual Day Window (days after last dose)
Last value on treatment			<7
Follow-up 1	7 days post-treatment	EOT + 7 days	7 – 13
Follow-up 2	14 days post-treatment	EOT + 14 days	14 – 16
Follow-up 3	17 days post-treatment	EOT + 17 days	17 – 20
Follow-up 4	21 days post-treatment	EOT + 21 days	21 – 23
Follow-up 5	24 days post-treatment	EOT + 24 days	24 – 27
Follow-up 6	28 days post-treatment	EOT + 28 days	28 – 41
Post safety follow up			≥42

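### The SAP's post-treatment windows for laboratory, weight and vital-sign data leave Day 27 after last dose unassigned, and an on-schedule Follow-up 4 in some early stoppers can fall on that day

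*SAP*

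**What the plan says.** Table 6.7: 9 in SAP section 6.7 has three rows, counted in days after last dose. The row for the first on-site follow-up visit covers seven days, from Day 13 to Day 19. The row for the second also covers seven days: "Follow-up 4 21 days post-treatment EOT + 21 days 20 – 26". The row for the last such visit has a lower bound only, and that bound is written as a strict inequality: "Follow-up 6 28 days post-treatment EOT + 28 days >27".

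The table's footnote limits its scope: "This analysis visit windows only apply to the post-treatment period defined in Table 6.1: 2". In SAP section 6.1 that period starts at "Date of the last treatment administration + REP + 1 day", and "the residual effect period (REP) is defined as 12 days after the last dose of trial medication". SAP section 6.7 maps unscheduled assessments together with scheduled ones. If several assessments fall in one window, it keeps only the one closest to the planned day, or the later one in a tie. As published, the section has no rule for a value that falls in no window. SAP section 7.8.2 plans a summary of post-treatment laboratory data.

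The visits themselves are timed from a different origin. For a patient who stops early, Protocol Flow Chart footnote 17 says "the eEOT visit must be performed within 7 days of study drug discontinuation", and section 6.2.3.4 counts those 7 days from the last dose. Footnote 18 says "Each follow-up visit is to be scheduled from the EOT or early EOT visit". The Flow Chart places Follow-up 4 at EOT or eEOT + 21 days (±1) and Follow-up 6 at + 28 days (+7 only). For completers, Protocol section 4.1.4 puts the last dose on the day before the EOT visit.

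**The concern.** The second window ends at Day 26 and the third starts after Day 27, so a value on Day 27 has no analysis visit. The on-treatment tables (6.7: 7 and 6.7: 8) cannot pick it up, because they are cut off at the end of the 12-day residual effect period. The parallel table for PWC-20 (6.7: 10) has no such gap: 24–27, then 28–41, then ≥42.

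This would not matter if no planned visit could fall on Day 27. But the windows count from last dose while the visits count from EOT or eEOT, and in early stoppers the two origins can be up to 7 days apart. At stake is the completeness of the descriptive safety summaries after stopping. In the Flow Chart, laboratory tests are optional at Follow-up 2 and required at Follow-up 4 and Follow-up 6, so Follow-up 4 is the first required draw of the safety follow-up. The values that could be left out come only from early stoppers, and haemoglobin is among them.

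**Working it through.** **1. Coverage of the windows.** The post-treatment period starts on Day 12 + 1 = 13 after last dose, which agrees with the lower bound of the Follow-up 2 row. From there:

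| Days after last dose | Analysis visit |
|---|---|
| 13–19 | Follow-up 2 |
| 20–26 | Follow-up 4 |
| 27 | none |
| 28 and later | Follow-up 6 |

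Day 27 is the only unassigned day.

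**2. Completers.** EOT = last dose + 1.

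- Follow-up 4: 1 + 21 ± 1 = Days 21–23.
- Follow-up 6: 1 + 28 + (0 to 7) = Days 29–36.

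Neither reaches Day 27.

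**3. Early stoppers.** Let d be the days from last dose to eEOT (0 to 7) and k the visit offset (−1, 0, +1).

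- Follow-up 4 day = d + 21 + k, range 20 to 29. It equals 27 when d + k = 6:
  - d = 5, k = +1: 5 + 22 = 27
  - d = 6, k = 0: 6 + 21 = 27
  - d = 7, k = −1: 7 + 20 = 27
- That is 3 of 8 × 3 = 24 on-schedule combinations (12.5%). None has d of 4 or less.
- Follow-up 6 day = d + 28 + (0 to 7), range 28 to 42, so it never falls on Day 27.

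**4. How many patients.** Protocol section 7.5 projects 30% to 40% early treatment termination among 586: 0.30 × 586 = 176 and 0.40 × 586 = 234. The distribution of d and attendance at Follow-up 4 are not given, so these are scenarios under assumptions:

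| Assumption | Patients with Follow-up 4 on Day 27 |
|---|---|
| Every eEOT within 4 days of last dose | 0 |
| d and k uniform, all early stoppers attend | 176 × 0.125 = 22 to 234 × 0.125 = 29 |
| d and k uniform, 25% to 50% attend | 176 × 0.25 × 0.125 = 5.5 to 234 × 0.50 × 0.125 = 14.6, about 6 to 15 |

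The 25% to 50% is borrowed from section 7.5, where it is the share of early dropouts expected to have efficacy outcomes after stopping. Using it for safety follow-up attendance is a rough proxy. All counts are across both arms.

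**5. Comparing the two ways of closing the gap.** Both assign Day 27. They differ under the rule that keeps one assessment per window. In the affected patients (d = 5 to 7), Follow-up 6 falls on Days 33 to 42.

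- *Follow-up 6 as ≥27.* The Day 27 Follow-up 4 and the true Follow-up 6 share a window. If the planned day is read as Day 28 after last dose, Day 27 is 1 day away and Follow-up 6 is at least 33 − 28 = 5 days away, so the three-week value takes the four-week label. If it is read as eEOT + 28, Follow-up 6 is normally kept and the Follow-up 4 value still goes unused.
- *Follow-up 4 as 20–27.* On-schedule Follow-up 6 starts at Day 28, so no compliant Follow-up 6 visit is relabelled. One competitor remains. Follow-up 2 = d + 14 + k falls on Days 18 to 22 for d = 5 to 7, and on Days 20 to 22 in 1, 2 and 3 of the 3 offsets for d = 5, 6 and 7 respectively, so 6 of 9. With the planned day read as Day 21 after last dose, such a Follow-up 2 value (at most 1 day away) is chosen over Day 27 (6 days away).

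**The case against.** The strongest reply is that this is a clerical slip in one descriptive table with almost no consequence. Much of that stands. Only values on exactly Day 27 are affected. They stay in the database. Day 27 lies inside the 4-week withdrawal period of SAP Table 6.1: 2 (Days 1 to 28 after last dose), and Protocol section 7.2.5 has that analysis cover vital signs. Laboratory shift tables use on-treatment values and do not change.

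A reader might infer that haemoglobin recovery after stopping is lost. The documents do not support that. Follow-up 6 includes laboratory tests and, on schedule, never falls on Day 27. Protocol section 5.2.6.4 also has both haematology panels repeated at subsequent visits after an alert, until alerts clear or the study ends.

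A reader might also take 22–29 as the expected number of patients. That figure needs uniform delays and full attendance, and the documents give neither. Patients may withdraw consent and have no further visits (Protocol section 3.3.4.3), or agree to limited safety contact only (Table 6.2.3.4: 1).

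It can also be said that the deeper cause is the mismatch of origins, last dose for windows and eEOT for visits, so that closing the gap recovers only part of the data. That is correct. A Follow-up 4 on Day 28 or 29 (3 of the 24 combinations) is still placed in the Follow-up 6 window.

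A lost equals sign in the reading of the PDF is unlikely, since ≥ survives in neighbouring tables, but the source should be checked.

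What the reply does not remove is that the rule, followed exactly, leaves out valid data from protocol-compliant visits, and that section 6.7 has no provision to catch them.

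**Conclusion.** The table is wrong as written, and the point is minor. Day 27 after last dose has no analysis visit, and an on-schedule Follow-up 4 falls there in some early stoppers whose eEOT visit is 5, 6 or 7 days after last dose. Those laboratory, weight and vital-sign values then drop out of the by-visit post-treatment summaries and nothing else. Completers are unaffected, and no efficacy estimate, test, type I error rate or power is involved.

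The number of patients cannot be derived from the documents. It ranges from none to about 22–29 under the assumptions shown, and is smaller with incomplete attendance. The count covers Follow-up 4 only. Unscheduled samples, and the regular trial visits that early stoppers continue to attend, could also fall on Day 27 and are not counted.

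**What to change.** In SAP Table 6.7: 9, change the Follow-up 4 window from 20–26 to 20–27 before treatment information is released. No day from 13 onward is then unassigned, and the Follow-up 6 window begins at Day 28, as it already does in Table 6.7: 10. Do not close the gap by writing ≥27 for Follow-up 6, for the reason in step 5 of the working.

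The cost is one bound in one table, with no change to trial conduct or data collection. The small downside is that recovery is not complete: for weight and vital signs, a Follow-up 2 on Days 20–22 may still be selected over a Day 27 Follow-up 4. Recovery is most complete for laboratory data, where the Follow-up 2 sample is optional. It would help to state in the same edit whether the planned day for these rows is counted from last dose or from EOT/eEOT, because the closest-to-planned-day choice depends on it.

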5.2.6.4 Haemoglobin and anaemia

To reduce bias on efficacy assessments, starting at visit 2 until the end of trial, **Haematology Panel A parameters** (refer table 5.2.3:1) will be blinded to the site and to the sponsor.

Clinical Trial Protocol

Page 64 of 112

Proprietary confidential information © 2023 Boehringer Ingelheim International GmbH or one or more of its affiliated companies

Sites will be alerted if the following occurs:

- Alert 1: Hb decrease > 20 g/L (2 g/dL) compared to baseline value
- Alert 2: The Hb value is below the normal reference range
- Alert 3: Hb value fulfils the criteria to withdraw the treatment (refer to section 3.3.4)

An independent third party will review both **haematology panels** throughout the trial. In addition, the independent DMC will review unblinded safety data on a regular basis throughout the study.

Scenarios and Actions:

Alert 1:

- Patients may continue on the study medication.
- Both haematology panels should be performed at the next visit (or earlier, per investigator's judgement). Both haematology panels should be repeated at subsequent visits until alerts are no longer triggered or once the end of study has been reached.

Alert 2:

- Patients may continue on the study medication.
- Both haematology panels should be performed at the next visit (or earlier, per investigator's judgement). Both haematology panels should be repeated at subsequent visits until alerts are no longer triggered or once the end of study has been reached.
- The investigator should further evaluate the patient status and report the AE "anaemia" based on investigator's clinical judgment. Once Alert 2 is no longer trigged, the investigator may evaluate whether or not the AE "Anaemia" is resolved.

For Alert 1 and/or 2, patients can be rolled over to the extension study. Details on monitoring of an ongoing adverse event "Anaemia" in the extension study will be provided in 1346-0014 study protocol [c33088336].

Alert 3:

- **Stop study medication.** Refer to section 3.3.4.2.
- Report as an AE "Anaemia"
- Both haematology panels should be performed at the next visit (or earlier, per investigator's judgement). Both haematology panels should be repeated at subsequent visits until alerts are no longer triggered or once the end of study has been reached.
- Patient should be referred to a specialist for further management.
- Patients are not eligible for the extension trial.

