6.2.5 Trial Completion

Each individual patient's end of study will depend on several factors including whether or not the patient completed the trial treatment plus the safety follow-up, or if the patient has prematurely discontinued treatment and either continued with trial participation or stopped trial participation early.

- Patients who complete 26 weeks of trial treatment and 4 weeks of safety follow-up: completion of follow-up visit 6 is considered to be the patient's end of study.
- Patients who prematurely stop the trial treatment and continue with trial participation: after completing the eEOT and the safety follow-up visits, the patient will be followed according to the flow chart until the planned V11 (26 weeks) or EOT +28 days, whichever is longer. The last study visit will be the end of study for that patient.
- Patients who prematurely stop the trial treatment and do not continue with trial participation: patients should be encouraged to complete the eEOT and safety follow-up visits, if possible. The last study visit will be the end of study for that patient.

Patients should continue to take their background therapy for schizophrenia, as prescribed by the investigator or treating physician.

AEs that are ongoing at the last Follow-up Visit should be followed up until they are resolved, have been assessed as "chronic" or "stable", or no further information can be obtained or deemed reasonably followed up by the investigator (refer to section 5.2.6.2.1).

Page 76 of 112

Proprietary confidential information © 2023 Boehringer Ingelheim International GmbH or one or more of its affiliated companies

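### The Follow-up 6 window for post-treatment laboratory, weight and vital-sign values has no upper day, so an early stopper without a Follow-up 6 sample can contribute a much later value to the 28-day row

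*SAP*

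**What the plan says.** SAP section 6.7, Table 6.7: 9, sets the post-treatment windows for laboratory values, weight and vital signs in days after last dose: Follow-up 2 is 13–19, Follow-up 4 is 20–26, and the last row reads "Follow-up 6 28 days post-treatment EOT + 28 days >27". The footnote adds: "This analysis visit windows only apply to the post-treatment period defined in Table 6.1: 2". SAP Table 6.1: 2 starts that period at "Date of the last treatment administration + REP + 1 day", with a residual effect period (REP) of 12 days, and ends it at "Date of the last per protocol visit".

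Within a window, SAP 6.7 takes the assessment closest to the planned day and maps unscheduled assessments along with scheduled ones. The on-treatment laboratory and vital-sign windows are cut at the end of the REP.

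The next table, for the PWC-20, handles the same visit differently. Follow-up 6 is 28–41 days after last dose, and a separate row, "Post safety follow up", begins at Day 42.

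Under Protocol 6.2.5, patients who stop treatment but remain in the trial are followed "until the planned V11 (26 weeks) or EOT +28 days, whichever is longer". Flow Chart footnote 16 lists what is dropped for them: "For patients who have permanently discontinued study medication the following procedures are no longer required: Dispense and administer IMP, IMP compliance check, AiCure review", then PK and biobanking samples. Safety laboratory tests are not on that list. After a haemoglobin alert, Protocol 5.2.6.4 adds: "Both haematology panels should be repeated at subsequent visits until alerts are no longer triggered", or until the end of study.

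**The concern.** The row label promises a value about four weeks off drug, but the rule admits anything from Day 28 to the patient's last visit. For completers the window closes itself, because Follow-up 6 ends their study. For early stoppers it does not: their later scheduled visits fall after the REP, cannot map to any on-treatment window, and so go to Follow-up 6.

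Two things follow. If the Follow-up 6 sample is missing, a later value stands in for it under the 28-day label. If it is present, the later values drop out of the by-visit summary. Haemoglobin is the parameter that matters most: its decrease is a listed risk with its own alerts and withdrawal criterion, and SAP 7.8.2 says post-treatment laboratory data will be summarised. If haemoglobin recovers off drug, late values would make the 28-day row look more favourable than it is.

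**Working it through.** The plan states no numerical result here to reproduce, so the check maps the visit schedule through the window rule.

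**Inputs.** Flow Chart: post-baseline safety laboratory days 43, 85, 127, 148 (haematology panels only), 169 and 183. SAP 6.1: REP 12 days. SAP Table 6.7: 9: windows as above. SAP 6.7: closest-to-planned-day rule.

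**Formula.** Days after last dose = visit day − last-dose day. Example: last dose on Day 22, Visit 6 on Day 85, so 85 − 22 = 63, which is more than 27 and maps to Follow-up 6.

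| Last dose (study day) | Scheduled laboratory values in the Follow-up 6 window (days after last dose) | Picked if no Follow-up 6 sample, all later visits attended | Picked if only Visit 11 attended |
|---|---|---|---|
| 22 | 63, 105, 126, 147, 161 | 63 | 161 |
| 43 | 42, 84, 105, 126, 140 | 42 | 140 |
| 64 | 63, 84, 105, 119 | 63 | 119 |
| 85 | 42, 63, 84, 98 | 42 | 98 |
| 106 | 42, 63, 77 | 42 | 77 |
| 127 | 42, 56 | 42 | 56 |
| 148 | 35 | 35 | 35 |

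Weight and vital signs are scheduled more sparsely (Days 64, 127 and 183), so their gaps can be wider. With last dose on Day 43, the first such visit in the window is at 127 − 43 = 84 days.

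**Latest compliant Follow-up 6.** The early end-of-treatment (eEOT) visit may be up to 7 days after last dose, Follow-up 6 is 28 days after that, and its visit window is +7: 7 + 28 + 7 = Day 42. For completers, the last dose is the day before EOT, so Follow-up 6 falls at 1 + 28 = 29 to 1 + 28 + 7 = 36 days after last dose.

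**Number of patients.** Protocol 7.5 projects 30–40% early termination and expects 25–50% of those patients to have efficacy outcomes afterwards, with 293 per arm. Assuming laboratory attendance is similar:
- low: 0.30 × 0.25 × 293 = 22 per arm with later visits
- high: 0.40 × 0.50 × 293 = 59 per arm
- at an assumed 20% without a Follow-up 6 sample: 0.20 × 22 = 4 to 0.20 × 59 = 12 values per arm

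The documents do not give the 20%.

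**Gap at Day 27.** The printed windows go from 20–26 to more than 27, so Day 27 belongs to no visit. It can occur: an eEOT visit 6 days after last dose puts Follow-up 4 at 6 + 21 = Day 27.

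**The case against.** The strongest reply is that the selection rule already contains most of the problem. Where a Follow-up 6 sample exists it will normally be the closest to the planned day, and Protocol 6.2.4 requires all safety follow-up visits. Mis-timing therefore needs a patient who stops early, misses Follow-up 6 and still gives a later sample. That stands, and it is why the count is small.

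It can also be said that open-ended last windows are this SAP's usual practice. But the open-ended on-treatment laboratory and vital-sign windows are cut at the end of the REP, and in the efficacy tables the open window belongs to the last planned assessment. For an early stopper, Follow-up 6 is often not the last visit.

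A reader might go further than the documents allow in three ways.
- Treating all early stoppers, 0.30–0.40 × 293 = 88–117 per arm, as exposed would give 18–23 mis-timed values per arm at the same 20%. Protocol 7.5 does not expect all of them to keep providing data.
- Protocol 3.2 does not make reversibility of the haemoglobin decrease a stated purpose of the 28 days. It speaks of unexpected side-effects and sends haemoglobin follow-up to section 5.2.6.4.
- The recovery of patients withdrawn for low haemoglobin is not lost altogether. Alert 3 is reported as an adverse event, adverse events are followed to resolution or stability (Protocol 5.2.6.2.2), and out-of-range values are highlighted in listings (Protocol 7.2.5). What is lost is their place in the by-visit summary.

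**Conclusion.** The point holds as a minor one. As written, the rule can report a laboratory value from Day 42 to 63 after last dose, and in the extreme about Day 161, as a 28-day value. This applies to early stoppers who stay in the trial without a Follow-up 6 sample. The working estimate is 4–12 values per arm, resting on two assumptions: that the efficacy-data retention rate carries over to laboratory visits, and that 20% of those patients lack Follow-up 6. The estimate leans high. It counts patients whose substitute falls at Day 42, no later than a compliant Follow-up 6 could fall, and patients with last dose on or after Day 141, for whom an on-schedule Visit 11 is at most 183 − 141 = 42 days after last dose.

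Only descriptive safety summaries are affected; efficacy and type I error are untouched. The direction for haemoglobin, towards apparent recovery, is plausible if levels recover off drug, but the documents give no basis for sizing it.

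**What to change.** Edit SAP Table 6.7: 9 as follows.
- Set Follow-up 6 to Days 28–42 after last dose.
- Add a post-safety-follow-up row from Day 43, as the PWC-20 table does in principle.
- Assign Day 27. Extending Follow-up 4 to 20–27 is the natural choice, since a compliant Follow-up 6 cannot fall before Day 28.

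Copying the PWC-20 limit of Day 41 would push a compliant Follow-up 6 on Day 42 into the later row, so Day 42 is the better cap. A scheduled visit that happens to fall on Day 42 would still count as Follow-up 6, which is tolerable. Because the planned day is counted from EOT and the window from last dose, a note should also say which origin decides closeness.

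The cost is one table edit and the matching programming, with no change to data collection.

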Proprietary confidential information © 2023 Boehringer Ingelheim International GmbH or one or more of its affiliated companies

If the positive report is confirmed, appropriate actions for the patient's safety have to be initiated and followed up as deemed necessary. The C-SSRS may be repeated at an unscheduled visit at the investigator's descretion.

C-SSRS results will be reported in terms of AEs as described in Section 5.2.6.1.4.

Penn Physician Withdrawal Checklist (PWC-20) is a short, reliable instrument that has been developed to detect potential treatment discontinuation (withdrawal) symptoms [R20-4170]. This 20-item questionnaire will be administered first at visit 10 or at the early EOT visit, for patients who prematurely discontinue study drug, and then during the 4-week follow-up period after termination of treatment with Iclepertin to collect potential symptoms and AEs related to dependence and withdrawal in a structured manner. Collection of AEs should be done before administering the PWC-20. Note: for AE reporting in eCRF and on SAE form (when applicable) the standards as outlined in section 5.2.6 apply. Symptoms that are exclusively determined to be due to the underlying disease without presenting any worsening, do not require AE reporting.

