6.2.3.4 Early permanent discontinuation from treatment

- Every effort should be made to collect data in all randomised patients. This includes randomised patients who never took the study medications and patients who permanently discontinued study drug.
- If a patient permanently discontinues the study medication, an eEOT visit must be performed within 7 days after the last dose of study medication. It is extremely important that patient should be encouraged to complete at least the MCCB, SCoRS and VRFCAT assessments. The reason for discontinuation of treatment must be recorded in the eCRF.
- The eEOT Visit can be split into 2 sequential days, in which case:
 - o The MCCB and VRFCAT should be performed on the first day;
 - o PRECIS should not take place immediately after MCCB, to avoid bias.

Page 74 of 112

- o The remaining assessments can be done per the convenience of the patient and site, either on the first day or the second day of the eEOT visit.
- To reduce burden on study partner, it is recommended to perform SCoRS on the same day.

- After the eEOT visit, patients should complete the safety follow-up visits and continue with the scheduled trial visits, until the end of the planned end of trial for that patient unless they withdraw consent to participate in the study.
 - o Refer to the Retention Guide in your ISF for further instructions.
- If it is not possible to complete all visits in clinic, at least phone contacts should occur at the scheduled visit time points. It is vital to explain to these patients the importance of continued trial participation. Additional information is provided in the ISF.
- When discussing options for continued trial participation, sites must present the first option to the patient and discuss this option thoroughly before presenting the next option for follow-up.
- Patients should be encouraged to choose the most rigorous follow-up regimen they are willing and able to comply with. The investigators should inform these patients that they will be allowed to change this regimen later if needed.
- Patients may choose to re-start the trial medication at any time during their planned treatment period as long as there is no safety concern, in the opinion of the investigator.

Table 6.2.3.4: 1 Follow-up of patients who prematurely discontinue the study treatment*

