In addition to the main safety analysis, withdrawal-related safety analysis will be conducted separately and descriptive for AEs emerging during the off-treatment safety follow-up period. New AEs emerging during this 4-week safety period, compared to while the patient is still on-treatment, will be identified and assessed by contrasting the following analysing treatment periods:

- 4-week withdrawal period for AEs occurring from 1 day after last dose to 28 after last dose of trial medication, and
- Strictly on-treatment period for AEs occurring from the start of treatment to the last dose of trial medication.

Page 84 of 112

Proprietary confidential information © 2023 Boehringer Ingelheim International GmbH or one or more of its affiliated companies

This withdrawal-related safety analysis will also assess vital signs descriptively.

Change in withdrawal symptoms based on PWC-20 will be analysed descriptively.

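### The PWC-20 on-treatment row in the SAP accepts values up to 6 days after the last dose, so patients who stop before Visit 10 may be compared with an off-drug reference while completers are compared with an on-drug one

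*SAP*

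**What the plan says.** **Windows.** In SAP 6.7, Table 6.7: 10 counts time under the column "Actual Day Window (days after last dose". Its first row, "Last value on treatment", covers fewer than 7 days and has no planned day. Follow-up 1 covers Days 7 to 13 and is described as 7 days post-treatment. When several values share a window, SAP 6.7 takes the one nearest the planned day and, in a tie, the later one.

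**Periods.** SAP Table 6.1: 2 ends the strictly on-treatment period on the date of last administration. It starts the 4-week withdrawal period at "Date of last treatment administration + 1 day". Protocol 7.2.5 has the matching period: "4-week withdrawal period for AEs occurring from 1 day after last dose to 28 after last dose of trial medication". The same SAP table also has a general on-treatment period that runs to the last dose plus the 12-day residual effect period (REP).

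**Collection.** Protocol 5.2 says of the PWC-20: "This 20-item questionnaire will be administered first at visit 10 or at the early EOT visit, for patients who prematurely discontinue study drug". The Flow Chart schedules it at Visit 10, eEOT and the six follow-up contacts, but not at EOT. On eEOT timing, protocol 6.2.3.4 says "an eEOT visit must be performed within 7 days after the last dose of study medication". Flow Chart footnote 17 waives the Visit 10 PWC-20 for patients who have already stopped permanently.

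**Analysis.** SAP 7.9 and protocol 7.2.5 promise a descriptive analysis of change in PWC-20 symptoms. The visible text does not say change from what.

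**The concern.** Protocol Table 1.4.2:1 acknowledges that adverse events after stopping the drug have not been formally studied, and lists the PWC-20 as a mitigation. Protocol 6.2.4 makes follow-up visits mandatory so that the effects of stopping can be evaluated. A change score answers that question only if its starting value was taken on drug.

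For a patient who stops before Visit 10, the only scheduled PWC-20 before follow-up is at eEOT, which may already be several days after the last dose. Any symptom that emerged by then would sit in the starting value and shrink the measured change. A summary that pooled these patients with completers would mix on-drug and off-drug references under one label. The possible error runs towards finding no withdrawal effect.

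**Working it through.** The plan states no figure for this point, so the check follows each type of patient through Table 6.7: 10.

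**Completers.** Visit 10 is planned for Day 169 and EOT for Day 183. The last dose is due the day before EOT (protocol 4.1.4), so about Day 182. Since 169 − 182 = −13, the Visit 10 value falls about 13 days before the last dose and is on drug.

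**Stopped before Visit 10, by day of eEOT after the last dose**

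| eEOT day | Row in Table 6.7: 10 | In withdrawal period (Days 1–28)? | Within 12-day REP? |
|---|---|---|---|
| 0 | on-treatment row | no | yes |
| 1 to 6 | on-treatment row | yes | yes |
| 7 | Follow-up 1 | yes | yes |

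On Days 1 to 6 the same day counts as withdrawal for adverse events and as on treatment for the PWC-20. Day 7 is allowed by the protocol, but there the only pre-follow-up value becomes a follow-up value and no scheduled reference remains.

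**Stopped between Visit 10 and EOT.** A Visit 10 value and an eEOT value on Days 0 to 6 both fall in the first row. The nearest-to-planned-day rule cannot choose between them because the row has no planned day. The word *Last* in its label implies that the eEOT value displaces the earlier, on-drug one.

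**A related mismatch.** Follow-up visits are scheduled from eEOT, but the windows count from the last dose. With eEOT on Day 3, nominal Follow-up 2 is on Day 3 + 14 = 17 and Follow-up 3 on Day 3 + 17 = 20. Both fall in the Follow-up 3 window (Days 17 to 20). Completers are not affected: EOT is 1 day after the last dose, so their visits are due on Days 8, 15, 18, 22, 25 and 29, each in its own window.

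**How many patients.** Protocol 7.5 projects 30% to 40% early termination:

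- 0.30 × 586 = 175.8, about 176
- 0.40 × 586 = 234.4, about 234

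The split by eEOT day is not given. For illustration only, assume that all attend eEOT and that none has a Visit 10 value:

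- Evenly over Days 1 to 7: 6/7 gives about 151 to 201 with an off-drug value in the on-treatment row, and 1/7 gives about 25 to 33 with no reference.
- Evenly over Days 0 to 7: 6/8 gives about 132 to 176, and 1/8 gives about 22 to 29.
- With half attending, each figure halves.
- If every eEOT were on the last-dose day, both counts would be zero.

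**The case against.** **The REP makes Days 1 to 6 on treatment.** The general on-treatment period in Table 6.1: 2 extends 12 days past the last dose, and protocol 1.2 expects drug levels or effects during that time. This stands against a stronger reading that a reader might infer, namely that the reference is already in withdrawal for every early stopper. A Day 0 value is on drug, and the documents do not show that symptoms have emerged by Days 1 to 6. It does not justify the row, however. A REP rule would cut at Day 12, whereas the table cuts at Day 7 and treats Days 7 to 13 as post-treatment.

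**The windows look deliberate.** Follow-up 1 is due 7 days after eEOT, so an eEOT on Days 0 to 6 puts it on Days 7 to 13, exactly the tabulated range. That explains the cut-off, but not the label or the Day 7 gap.

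**The withdrawal period is defined for adverse events.** This is correct, and using the first row as the reference for change is an inference, as is pooling. But protocol 7.2.5 places the PWC-20 sentence in its withdrawal-related section, and no other scheduled pre-follow-up value exists. Footnote 13 on the PWC-20 row and SAP 5.4 are not visible in the public copies and could add detail.

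**The schedule is the root cause.** This stands. No SAP window can create an on-drug value that was never collected, and a narrower row removes some patients from the change summary.

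**The consequence is limited.** This also stands. The analysis is descriptive, and adverse events are still analysed from the day after the last dose.

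**Conclusion.** The point holds in a limited form. The cut-off in Table 6.7: 10 matches neither of the SAP's definitions of on-treatment. It can place off-drug values under an on-treatment label, in patients who stop before Visit 10 and possibly in those who stop between Visit 10 and EOT. It also leaves a Day 7 eEOT and the Visit 10 versus eEOT choice unresolved.

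The bias is conditional: change is understated only where eEOT falls on Days 1 to 6 and symptoms have emerged by then. It should not be read as affecting all early stoppers.

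The 176 to 234 projected early stoppers cover both arms and are a ceiling, not a count of affected patients. A drug-withdrawal effect can arise only on iclepertin, which at 293 per arm and equal stopping rates means about 88 to 117 (0.30 × 293 = 87.9; 0.40 × 293 = 117.2). The illustrative counts under the working rest on assumed timing and attendance. They also ignore stoppers who have a Visit 10 value.

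The change is worth making before unblinding because it is cheap and the PWC-20 is the structured withdrawal instrument. It does not touch efficacy inference or type I error.

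**What to change.** Amend SAP 6.7 and 7.9, unless text not visible here already does so:

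- Reserve the on-treatment row for assessments on or before the last-dose date, and use the Visit 10 value when one exists.
- Put eEOT values taken on Days 1 to 7 after the last dose in a separate row, for example *eEOT, off drug, before follow-up*. This also settles the Day 7 case.
- Name the reference used for change.
- Report completers and early stoppers separately. Show change from on-treatment only for patients with an on-drug value. For the others, show PWC-20 levels by day since last dose and by arm, with change from eEOT shown separately and labelled as such.

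The cost is SAP wording, one extra descriptive row and a split table. The real downside is that patients who stop before Visit 10 and attend eEOT after their last dose no longer contribute to the on-treatment change summary. Their data remain visible as levels and as change from eEOT.
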